# Interventions

In this study investigators are choosing two TJM + exercise or two mobilization + exercise group appointments followed by three exercise only appointments consistent with clinical practice and similar research. In the original derivation study, Puentedura et al found that those individuals with 3 or more of the 4 clinical attributes were positive on the proposed clinical prediction rule, were 13.5 times more likely to improve with the probability of success improving from 39% to 90%. Two treatments were used to develop the clinical prediction rule. To maintain consistency, investigators will perform cervical TJM or NTM as the comparison treatment during the initial two visits. Additionally, this is consistent with other validation studies using two treatments focusing on cervical TJM to validate or fail to validate the original derivation findings.

Patients in both groups will attend physical therapy twice weekly during the first week and then once weekly for the next 3 weeks for a total of 5 sessions. Provider contact time of approximately 25 minutes per session will not differ between groups in treatments #1 and 2, as well as contact time of

approximately 45 minutes per session in treatments #3, 4, and 5. as detailed below.

MTE Intervention	Approximate Provider Contact Time	MoE Intervention	Approximate Provider Contact Time		
Warm-up E		
 
Supine cervical mobilizations (Grade I or II)
 
General mobility exercise (3-finger exercise for cervical rotation)
 
Advice to maintain usual activity
 
	
 
15 minutes (mobilizing at affected levels)
 
5 minutes (gradually progressive movement)
 
5 minutes
 
		
Two visits	Total/visit = 25 minutes	Two visits	Total/visit = 25 minutes		
	
 
Warm-up E
 
Stretching and Streng
 
Advice to return to usual p
 
Three
 
	sions #3, 4, and 5 xercises (10 minutes) (thening Exercises (30 minutes) hysical work and activity (5 min e visits = 45 minutes			

# MTE Group

The treatment program consists of three components: 1) cervical TJM, 2) a general mobility exercise (three-finger cervical rotation exercise), and 3) advice to maintain usual activity within the limits of pain.

# Treatment Session #1

Cervical TJM: The patient will receive a supine cervical TJM directed to an appropriate level between C3 and C7. Clinicians will be allowed to use discretion as to which level they feel is more restricted, and they will then perform a cervical TJM technique to each side of the cervical spine. They will be allowed to perform a maximum of two attempted TJMs to each side. The investigators are intentionally selecting manipulative interventions that can easily be performed, in order to increase the generalizability of the CPR that was developed. In addition, patients will be instructed in a basic cervical mobility exercise (Appendix F) and instruction to maintain usual activity level within the limits of pain. The following is a detailed description of the steps involved in performing TJM to the cervical spine:

# C3 – C7 Upslope Glide – Cradle or Chin hold

Steps: (L rotation – R side upslope glide C4 example)

The patient is positioned comfortably in supine with the neck in a neutral relaxed position on a pillow. The therapist stands at the head of the plinth; feet spread slightly and apply their contact point on the posterolateral aspect of the right C4 articular pillar. The therapist's hand applicator is the lateral border of the proximal or middle phalanx. For the cradle hold, the weight of the patient's head and neck is balanced between the therapist's left and right hands, with

cervical positioning controlled by converging pressure from both hands. The therapist then introduces primary leverage of rotation to the left and a small degree of secondary leverage of side bending right while maintaining the contact point on the posterolateral articular pillar. The TJM is directed upwards and towards the patient's left eye while simultaneously applying a slight, rapid increase of rotation of the head and neck to the left with no increase of side bending to the right.

# C3-C7 Upslope Glide - Cradle or Chin hold (alternate technique)

Steps: (R rotation – L side upslope glide C4 example)

The patient is positioned comfortably in supine with the neck in a neutral relaxed position on a pillow. The therapist stands at the head of the plinth; feet spread slightly and apply their contact point on the posterolateral aspect of the left C4 articular pillar. The therapist's hand position is applied through the lateral border of the proximal or middle phalanx. For the cradle hold, the weight of the patient's head and neck is balanced between the therapist's left and right hands, with cervical positioning controlled by converging pressure from both hands. The therapist then introduces primary leverage of rotation to the right (30-40 degrees) and a small degree of secondary leverage of sideshift to the right and side bending left while maintaining the contact point on the posterolateral articular pillar. The TJM is directed upwards and towards the patient's right eye while simultaneously applying a rapid increase of rotation of the head and neck to the right with no increase of side bending to the left.

# Treatment Session #2

The second treatment session will occur within 2-4 days after the first session. Prior to beginning treatment session #2, all patients will complete the patient GROC to determine whether they experienced a clinically meaningful improvement. Perceived recovery will be used because the Neck Disability Index has been criticized for not adequately capturing low levels of disability (potential for a floor effect) and for not being responsive to small, but clinically important, changes in patients with low levels of initial disability.

Interventions provided for treatment session #2 will be identical to treatment session #1, consisting of three components: 1) cervical TJM, 2) a general mobility exercise (three-finger cervical rotation exercise), and 3) advice to maintain usual activity within the limits of pain.

# Treatment Sessions #3, 4, and 5:

The treatment program consists of three components: 1) warm-up exercises for 10 minutes, 2) a program of stretching and strengthening exercises for the cervical, thoracic and shoulder complex, and 3) advice to return to usual physical, work and recreational activity.

The third and subsequent treatment sessions will occur within 5-7 days of each previous treatment session. At each of these treatment sessions, patients will complete a GROC based on their

perceived recovery since the baseline examination. As well as the GROC, all patients will complete a follow up NPRS, FABQ and NDI at the beginning of visits #3 (1 week) and #5 (1 month).

### Warm-up Exercises:

Patients/ therapists will be allowed to choose between gentle overhead pulley work, upper body ergometer and/or bicycle ergometer for a combined total of 10 minutes.

# Stretching and Strengthening Exercises:

Patients/ therapists will be allowed to choose from the exercises depicted in the table below. They must choose at least 5 exercises from each of the 2 groups and perform exercises for a total time of 30 minutes.

Stretching Group	Strengthening Group
Upper Trapezius Stretch	Deep neck flexor training
Scalene/Sternocleidomastoid stretch	Isometric strengthening
Levator scapulae stretch	Middle trapezius strengthening in prone
Pectoralis Major and Minor stretch	Lower trapezius strengthening in prone
Cervical AROM with ball on wall	Serratus wall push-ups
Cervical AROM with laser headband	Seated cable rows
Upper cervical F/E with hands behind neck	Seated lat pulls
Lower cervical F/E with hands behind neck	Standing tall boys
Shoulder shrugs (Scapular clock)	Standing lawn mower pull starts
Shoulder horizontal ABD/ADD with hands behind neck	

# MoE Group

The treatment program consists of three components: 1) cervical NTM Grade I/II, 2) a general mobility exercise (three-finger cervical rotation exercise), and 3) advice to maintain usual activity within the limits of pain.

# Treatment Session #1

Mobilizations: The patient will receive Grade I or II to an appropriate level between C3 and C7. Clinicians will be allowed to use discretion as to which level they feel is more restricted, yet they will use NTM Grade I or II not progressing to joint resistance. Grade I and II NTM are used to reduce pain and irritability and serve as a control. Grade I NTM will consist of small amplitude movements of the spine or joint that are performed at the beginning of the joint's range of motion. These movements are performed with light pressure and slow oscillations. Grade II NTM will consist of larger amplitude movements that occur within the joint's available range of motion, avoiding initial joint resistance. In addition, patients will be instructed in a basic cervical mobility exercise (Appendix F) and instruction to maintain usual activity level within the limits of pain. The following is a detailed description of the steps involved in performing low-grade mobilizations (NTM):

# C3-C7 Grade I or II prone posterior to anterior (PA) mobilizations:

Steps: (Central PA mobilization - C4 example)

The patient is positioned comfortably in prone with the neck in a neutral relaxed position. The therapist stands at the head of the plinth; feet spread slightly. The therapist's contact point is the spinous process of the target cervical vertebra, using the pads of their thumbs. Maintaining the cervical spine in neutral, the therapist applies a non-thrust central PA mobilization using a non-thrust low-grade mobilization (Grade I or II).

For Grade I, the therapist performs small-amplitude movements at the beginning of the range of motion, creating a gentle oscillatory pressure on the spinous process. For Grade II, larger-amplitude movements are performed within the free range of motion, without moving into resistance or stiffness. The therapist will perform 30 second bouts of mobilizations at each restricted level of the cervical spine to minimize the potential for an "attention effect," comparatively between the cervical TJM and NTM groups.

# Treatment Session #2

The second treatment session will occur 2-4 days after the first session. Prior to beginning treatment session #2, all patients will complete the patient GROC to determine whether they experienced a clinically meaningful improvement.

Interventions provided for treatment session #2 will be identical to treatment session #1 consisting of three components: 1) Low grade cervical NTM, 2) a general mobility exercise (three-finger cervical rotation exercise), and 3) advice to maintain usual activity within the limits of pain.

# Treatment Sessions #3, 4, and 5

To ensure equal comparison and attention effect, the treatment administered in treatment sessions #3, #4 and 5, will be conducted according to the same protocol as the MTE group. The treatment program consists of three components: 1) warm-up exercises for 10 minutes, 2) a program of stretching and strengthening exercises for the cervical, thoracic and shoulder complex, and 3) advice to return to usual physical, work and recreational activity.

The third and subsequent treatment sessions will occur within 5-7 days of each previous treatment session. At each of these treatment sessions, patients will complete a GROC based on their perceived recovery since the baseline examination. As well as the GROC, all patients will complete a follow up NPRS, FABQ and NDI at the beginning of visits #3 and #5.

# Warm-up Exercises:

Patients/ therapists will be allowed to choose between gentle overhead pulley work, upper body

Page 22 of 45

ergometer and/or bicycle ergometer for a combined total of 10 minutes.

# Stretching and Strengthening Exercises:

Patients/ therapists will be allowed to choose from the exercises depicted in Figure 4. They must choose at least 5 exercises from each of the 2 groups and perform exercises for a total time of 30 minutes.

If a participant terminates their involvement early, the results from their last appointment will be carried forward within the intention-to-treat analysis. The participant may pursue any and all healthcare treatment they would like upon termination or completion of the treatment portion (visits 1-5) of the study.

			-						
	Prior to	Visit	Visit 2	Visit 3	Visit	Visit 5	1 month	3-month	6-month
	Visit 1	1		(1 week)	4		follow-up	follow-up	follow-up
Treatment		Х	Х	Х	Х	Х			
Pre-Screen	Х								
Eligibility		Х							
Screening									
Medical		Х							
History									
Baseline		Х							
Assessment									
Demographics		Х							
Pain Diagram		Х		Х			Х	Х	Х
NDI		Х		Х			Х	Х	Х
NPRS		Х		Х			Х	Х	Х
GROC			Х	Х	Х	Х	Х	Х	Х
FABQ		Х		Х			Х	Х	Х

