- 11. Inability to legally provide informed consent for any other reason.
- 12. Inability to comply with the treatment and follow-up schedule.

Due to the unknown effect of cervical TJM in pregnancy due to a lack of rigorous scientific research, women who are known to be pregnant or lactating will not be included in this study. If an individual becomes pregnant during the first month of the study, investigators will discontinue their manual therapy treatment but continue follow-up assessments in accordance with the intention-to-treat protocol.

Once patients are admitted to the study, no patient will be removed for non-compliance. Use of medication will not be controlled. However, to minimize its effect, patients will be instructed to continue taking their current medications as prescribed and not to start any new medications during the one-week and 4-week follow-up period. Current medication usage will be recorded at baseline. Additionally, at the 3 and 6-month follow-up investigators will collect data on medication usage as well as additional physical therapy visits and other healthcare interventions the patient may have received.

This study will include both genders and members of minority groups. The investigators will attempt to recruit patients in respective proportion to the demographics of each of the data collection clinic's respective geographic locations. No individuals will be excluded from participation in this study on the basis of race, creed, color, gender, national or ethnic origin, sexual orientation, disability, or health status.

Patients attending for physical therapy at any one of the 4 clinical sites will be screened for eligibility to participate in the study (neck pain duration of <38 days, once treatment blocks are filled for those subjects negative on the CPR). Physical Therapists trained in the study protocol will further evaluate participants by completing a medical screening process and a detailed history and physical examination for inclusion and exclusion criteria and obtain informed consent. Informed consent will be obtained within a private office setting. Subjects will have an opportunity to fully review the informed consent, ask questions, and determine independently if they want to participate in the research study.

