# 4. Intention-to-treat analysis

The study will use an intention-to-treat analysis, where all participants are analyzed in the group to which they were originally assigned, regardless of whether they completed the treatment as planned. This approach helps to avoid bias introduced by dropout or non-

compliance, ensuring that the results reflect the effectiveness of the interventions under typical clinical conditions.

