# Data Analysis:

Descriptive statistics, including frequency counts for categorical variables and measures of central tendency and dispersion for continuous variables will be calculated to summarize the data. Baseline demographic data will be compared across treatment groups. The investigators will compare baseline variables between groups by using independent t-tests or Mann–Whitney U tests for continuous data and chi-square tests of independence for categorical data. If analysis of baseline data suggests randomization did not reasonably control for potential confounders, those covariates will be included in models to adjust for confounding variables. If appropriate, statistical adjustments will be made for baseline characteristics that are significantly different between groups. An intention-to-treat analysis will be utilized, in which all participants will be analyzed in the group to which they were originally assigned. All drop-outs and the reason for dropping out of the study will be reported. An *a priori* alpha level of 0.05 will be used for all analyses. All data will be screened to ensure they meet the assumptions for the inferential statistical analyses described below. If they do not meet the necessary assumptions, appropriate nonparametric procedures will be utilized.

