Specific Aims: Primary Aim #1: To determine the validity of the clinical prediction rule for identifying patients with neck pain who are likely to benefit from C-TJM. Pain and Disability. The investigators will examine the primary aim with separate random intercept linear mixed models with treatment group (MTE vs. MoE), status on the CPR (positive or negative) and time (baseline, 1-week and 4weeks) as fixed effects. The dependent variables will be pain (NPRS) and disability (NDI score). The hypothesis of interest is the group \* CPR status \* time interaction. The primary dependent variables are the 1-week NPRS and NDI scores to mirror the follow-up used in Cleland and colleagues' study. The investigators will assess the NPRS and NDI scores after 4 weeks to determine whether a patient's status on the rule predicts outcome at a longer follow-up. The investigators will perform planned pairwise comparisons at each follow-up period by using the Bonferroni test of inequality. The investigators hypothesize that patients who are positive on the rule and receive TJM will achieve greater improvement in immediate (1-week) and 4-week pain and disability, than patients who are negative on the rule and receive TJM, and compared to patients who are positive on the rule but receive an alternative exercise program without TJM. Because the rule is believed to be specific to a TJM intervention, investigators hypothesize that outcomes among those receiving the MoE treatment would not differ on the basis of a patient's status on the rule.

Secondary Aim #1: To compare the long-term (6-month) pain and disability scores (clinical

outcomes) and healthcare utilization based on status on the clinical prediction rule and the treatment received. The investigators will examine this with random intercept linear mixed models with treatment group (MTE vs. MoE), status on the CPR (positive or negative), and time (baseline and 6-months) as fixed effects. The dependent variables will be pain (NPRS) and disability (NDI) scores. The investigators will perform planned pairwise comparisons at each follow-up period by using the Bonferroni test of inequality. The hypothesis of interest is the group \* status on CPR \* time interaction. The investigators hypothesize that patients who are positive on the rule and received TJM would experience greater improvement at 6-months than patients who are negative on the rule and received the MoE program without TJM.

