The investigators will also examine healthcare utilization using a two-way ANOVA comparing the number of healthcare visits post-treatment sessions with treatment group (MTE vs. MoE) and status on the clinical prediction rule (positive or negative) as independent variables. If appropriate, the interaction effect of the two independent variables will also be accounted for in the analysis. The dependent variable is the number of healthcare visits after completion of the treatment. The investigators hypothesize that patients who are positive on the rule and received TJM utilize less additional healthcare visits after completion of the treatment than patients who are negative on the rule and received the MoE program without TJM.

Secondary Aim #2: To compare changes in GROC and fear-avoidance beliefs at long-term follow-up (6-month) based on status on the clinical prediction rule and the treatment received. The investigators will examine this with separate random intercept linear mixed models with treatment group (MTE vs. MoE), status on the clinical prediction rule (positive or negative), and time (baseline and 6-months) as fixed effects. The dependent variables will be GROC changes and fear avoidance beliefs. The hypothesis of interest is the group \* status on CPR \* time interaction. The investigators will perform planned pairwise comparisons at each follow-up period by using the Bonferroni test of inequality. The investigators hypothesize that patients who are positive on the rule and received TJM would experience greater reduction in pain and fear avoidance beliefs than patients who are negative on the rule and received TJM, compared with patients who are positive on the rule but received the MoE program without TJM.

Missing Data. While analysis using mixed models allows all observed data to be included in the analysis under the assumption that the data are missing at random, if substantial missing data occurs, multiple imputation or mean conditional imputation will be used with subsequent sensitivity analyses to explore the impact of imputation on results. To address the issue of artificially reduced estimates of stochastic uncertainty produced by imputation, bootstrapping procedures will be used on the entire imputation and estimation process.

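### Early leavers' scores are carried forward in one section and left to a missing-at-random mixed model in another, and nothing says which rule governs the primary analysis

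*Combined protocol and SAP*

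**What the plan says.** Two sections of the combined protocol and SAP deal with participants whose data stop early.

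- **Section 5.0, MoE Group, after the exercise list:** "If a participant terminates their involvement early, the results from their last appointment will be carried forward within the intention-to-treat analysis". The sentence carries no condition and no exception.
- **Section 7.0, Missing Data:** "mixed models allows all observed data to be included in the analysis under the assumption that the data are missing at random". It then adds a fallback: "if substantial missing data occurs, multiple imputation or mean conditional imputation will be used with subsequent sensitivity analyses". It gives no threshold for invoking the fallback and does not mention carry-forward.

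The other references to intention-to-treat do not settle the matter. Section 4.0, item 4, says "all participants are analyzed in the group to which they were originally assigned", and section 7.0, Data Analysis, says the same: "An intention-to-treat analysis will be utilized, in which all participants will be analyzed in the group to which they were originally assigned". Both concern group membership, not missing scores. In section 3.0, participants who become pregnant in the first month stop manual therapy but "continue follow-up assessments in accordance with the intention-to-treat protocol".

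On endpoints, section 7.0, Primary Aim #1, says "The primary dependent variables are the 1-week NPRS and NDI scores", and later, "The investigators will assess the NPRS and NDI scores after 4 weeks". Section 5.0 has the 1-week survey completed before the third treatment. The schedule table and Appendix G list only the GROC at visit 2.

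**The concern.** A missing score cannot be both filled with the last value and left unfilled for a likelihood-based model. With two rules in force, no ranking between them and an undefined trigger for a third route (multiple or mean conditional imputation), the handling of missing primary data could be settled after the results are known.

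The carry-forward rule is also a poor default here. Section 5.0, in discussing how a success was defined, acknowledges that neck pain tends to improve on its own. In an improving condition, a carried-forward score understates improvement within a cell. If loss is equal across cells, a true difference shrinks. If loss is unequal, a difference can appear where none exists. For the primary variables the carried value is the baseline score for everyone lost before visit 3, so the assigned 1-week change is exactly zero.

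**Working it through.** **Inputs.** From section 7.0, Sample Size and Power: SD of NDI change 12, target difference 10, two-sided alpha 0.05, power 90%, 31 per cell, 140 recruited in four equal cells (35 each). That section does not say whether NDI points are on the 0–50 or the percentage scale; the same unit is used below. From section 5.0: visit 2 falls 2–4 days after visit 1, and each later visit 5–7 days after the one before. Loss rates and mean improvements below are assumptions, because the documents give neither. Loss is taken as unrelated to outcome.

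**1. The plan's own figure.** n = 2(1.96 + 1.2816)² × 12² / 10² = 30.3, so 31 per cell, which reproduces. The margin is 140 − 4 × 31 = 16 patients, or 16/140 = 11.4% (4 of 35 per cell). It is meant to cover distribution discrepancies as well as dropout.

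**2. What is available to carry forward.** Counting from the first treatment, visit 3 falls on days 2 + 5 to 4 + 7, that is 7–11.

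| Last visit attended | Last NDI/NPRS held | Effect of carry-forward |
|---|---|---|
| 1 | Baseline | 1-week change = 0 |
| 2 (GROC only) | Baseline | 1-week change = 0, by stepping back to the last available score |
| 3 or later | 1 week or later | 1-week score unaffected; later scores frozen |

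**3. Equal loss before visit 3.** If k of 35 are lost in each cell, a true difference of 10 becomes 10 × (1 − k/35): 9.7 for k = 1, 9.4 for k = 2, 8.9 for k = 4.

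**4. Unequal loss, no true difference.** With a common improvement of 10 and losses of 2 and 5 of 35, the false difference is 10 × (5 − 2)/35 = 0.86. The full-data standard error is √(2 × 144/35) = 2.87.

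**5. Unequal loss, true difference 10.** Suppose the cells improve by 15 and 5. Losing 4 of 35 only in the better cell gives 15 × 31/35 − 5 = 8.29. Losing 4 of 35 only in the comparator gives 15 − 5 × 31/35 = 10.57. The bias can go either way.

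**6. The three-way interaction.** Equal loss multiplies every cell's mean change by the same factor. If only the rule-positive manipulation cell gains an extra 10 points, an interaction of 10 also becomes 8.86 at 4 of 35.

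**7. Power.** With share d set to zero change, a cell with mean improvement m has variance (1 − d) × 144 + d(1 − d)m². Take d = 4/35 and cells improving by 10 and 0. The variances are 137.7 and 127.5, the standard error is √((137.7 + 127.5)/35) = 2.75, and power is Φ(8.86/2.75 − 1.96), about 89.6%. If the comparator improves by 5 or 10, power is 87.9% or 85.0%. Observed data (31 per cell) give 90.7%. At 20% loss the figures are 85.4% down to 76.6% under carry-forward, and 87.7% with observed data.

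**8. Four weeks, loss after visit 3.** With no true difference, a further common gain of g after week 1 and losses of 2 and 5 of 35, the false difference is g × 3/35: 0.17 for g = 2, 0.43 for g = 5.

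**9. Simulation check.** Settings: two cells of 35, random-intercept model at baseline, 1 and 4 weeks, variance components 72 and 72 treated as known, 4,000 runs, Monte Carlo error about 0.05.

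| Scenario | Observed data | Carry-forward |
|---|---|---|
| 1 week, true 10 (improvements 10 and 0), 4 lost per cell | 9.94 | 8.80 |
| 1 week, true 0, 2 and 5 lost | −0.06 | 0.81 |
| 4 weeks, true 0, 2 and 5 lost after visit 3, g = 5 | 0.04 | 0.47 |

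**10. A related mismatch.** Treatment Sessions #3, 4, and 5 (both groups) collects NDI, NPRS and FABQ at visit 5. The schedule table and Appendix G list only the GROC there. The last score held after visit 5 therefore depends on which section is followed.

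**The case against.** The best reconciliation is to read the section 5.0 sentence as the specific rule for early terminators and the Missing Data paragraph as the general rule for everything else. The documents do not say this, and if they did, carry-forward would enter the primary analysis for the very participants it distorts.

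Several narrower objections have force:

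- Read literally, the last appointment of someone who leaves after visit 2 yields no NDI or NPRS. Zero change for that person requires stepping back to baseline, a step the plan does not spell out.
- The pregnancy provision concerns people who stay in follow-up, so it does not bear on precedence.
- The hypothesis of interest is the three-way interaction. In the null example, the same 2-versus-5 imbalance by arm in both rule strata cancels: 0.86 − 0.86 = 0. A false interaction there needs the imbalance to differ by rule status, to which treating therapists are blinded. The pairwise comparisons are nevertheless planned analyses, and equal-loss attenuation does reach the interaction (step 6).
- The false 0.86 is only about 0.3 of a standard error (0.86/2.87), enough to move a 5% two-sided test to about 6%.
- The simulation favours observed data by construction, since loss is unrelated to outcome. If people leave because they recovered or failed to improve, neither method is assured and the direction of bias is not fixed.
- The Missing Data paragraph promises sensitivity analyses and bootstrapping of the imputation process. These apply to its own imputation route, not to the carry-forward sentence.
- The visit-5 timing gap is minor. The stated intervals put visit 5 on days 17–25 from first treatment, or up to day 27 from baseline if treatment starts 48 hours later, against a label of 1 month.

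These points limit the size of the problem. They do not remove the conflict.

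**Conclusion.** The concern holds and should be fixed. Two incompatible rules for early leavers stand in the current text, neither is ranked, and one of them assigns zero 1-week change on the primary variables to anyone lost before visit 3. The numerical effect is modest under small, balanced loss: at 4 of 35 per cell, a true 10-point difference falls to 8.9, and power is 85.0% to 89.6% instead of 90.7%. It grows with higher loss and can go in either direction with unequal loss. These sizes rest on assumed loss rates, assumed mean improvements and loss unrelated to outcome. The lack of a single prespecified primary method does not depend on those assumptions.

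**What to change.** - **Section 5.0:** delete the carry-forward sentence and state that early terminators contribute all their observed data to the mixed models.
- **Section 7.0, Missing Data:** name the mixed model on observed data, under missing at random, as the primary analysis. Make any imputation a labelled sensitivity analysis, so that the undefined trigger cannot change the primary result. Carry-forward, if kept at all, belongs only there.
- **Visit 5:** reconcile Treatment Sessions #3, 4, and 5 (both groups) with the schedule table and Appendix G on whether NDI, NPRS and FABQ are collected at that visit.

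The cost is one sentence replaced, one edited and one schedule reconciliation. It needs no new data or patients, and the Primary Aim #1 models and interaction test stay as they are.
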